4.1 Design Overview

This will be a prospective, multicenter, single-arm study.

4.2 Number of Subjects

The number of subjects in this study will be limited by the number of subjects who were randomized to the Control Group in the Lung Volume Reduction Coil Treatment in Patients with Emphysema (RENEW) Study, who completed the RENEW Study, and wish to participate in this crossover study, who provide written informed consent for this study, and who meet the inclusion and exclusion criteria of this study.

4.2.1 Pharmacological Treatment

As recommended by the GOLD guidelines, each subject will continue maintenance bronchodilator therapy, which will include an inhaled long-acting beta-agonist, inhaled anticholinergic, or both. These drugs may also be combined with theophylline and/or inhaled corticosteroids at the discretion of the treating physician. The physician will be allowed to adjust the subject's pharmacological regimen as needed during the course of the study to deal with variations in the subject's condition (e.g., COPD exacerbations). However, the subject's medical regimen should be optimized at the pre-Treatment Visit, prior to completing the baseline Six Minute Walk Test and pulmonary function tests. From then on, changes to their medical regimen should be discouraged during the follow-up period. Changes in medications or dosages will be recorded in the eCRF.

All subjects enrolled in the study must have current influenza and pneumococcus vaccinations consistent with local recommendations and/or policy.

4.3 Population

The study population will include all subjects who have met the inclusion/exclusion study criteria defined in this protocol.

4.4 Demographic and Baseline Characteristics

Demographics and subject characteristics at baseline will be summarized to include age at enrollment, sex, and ethnic origin.

4.5 Safety Evaluation

Safety will be evaluated by collection of AEs and SAEs from entry into the study (Visit 1) until Visit 10 (12 months Follow-up from Visit 2) or until the subject has completed or terminated from the study.

Prior to discharge after treatments and at each phone call or follow-up visit, subjects will be instructed to report to the investigator any adverse physical or mental changes they experienced since the previous visit/interview. All such AEs/SAEs reported by the subjects or observed by the investigators will be recorded.

Safety data from the various OUS studies that PneumRx has conducted to date have been collected and analyzed. A summary of the safety data is provided in Section 2.4, above.

4.6 Brief Description of Study

The complete Study and its required visits, procedures, and assessments will be carefully discussed with the study subjects using an Institutional Review Board (IRB) or an Ethics Committee (EC) approved Informed Consent Form (ICF). The ICF will contain all essential elements including a description of the research, expected duration and procedures, alternative treatments including lung volume reduction surgery, statement of the subject's right to decline to participate or to withdraw from the study at any time and for any reason without fear of retribution. The ICF will also include potential risks, discomforts or adverse effects, potential benefits, limits of confidentiality, reimbursement of certain expenses for participation, timely dissemination of any new information that becomes available, and contact information of the research personnel. All patients will sign an ICF prior to any additional procedures being performed to evaluate their eligibility for participation in the Study.

End of study data from the 12 Month Visit of the RENEW Study will be obtained to complete RENEW participation. At the end of the 12 Month Visit, RENEW participants who meet inclusion and exclusion criteria for this study will be offered participation that begins with signing a new ICF. Medical history, physical exam, and smoking history will be collected to ensure the subject meets inclusion and exclusion criteria. Spirometry must be repeated after the RENEW Study 12 Month visit as both pre- and post-bronchodilator data must be collected at Baseline for the Crossover Study. Only post-bronchodilator spirometry is collected at the 12 Month visit for the RENEW Study. However, the PFT excluding spirometry, DLCO, 6MWT, mMRC, and SGRQ data collected for the 12 Month Visit of the RENEW Study will be reviewed and used as Baseline data for this Study, unless the 12 Month RENEW data was taken more than 6 weeks previously, in which case such tests/questionnaires are be performed again, and data collected. If the subject does not meet the inclusion / exclusion criteria the subject will be excluded from the study.

If the subject has met the inclusion / exclusion criteria for this study, the subject will continue the screening evaluation to ensure they meet the remaining inclusion / exclusion criteria. The investigator will perform other tests such as spirometry, CT scan, X-ray, echocardiogram, EKG, and blood tests.

Once the subject has completed the pre-treatment tests and meets all inclusion / exclusion criteria, the subject will proceed to treatment.

4.6.1 Treatment

For each treatment, subjects will undergo bronchoscopy under general anesthesia or moderate sedation, at the discretion of the bronchoscopist. During both procedures, subjects will be treated with Coils according to the Instructions for Use. Subjects will receive prophylactic drugs pre-procedure and post-procedure.

Following LVRC placement (Visit 2), the subject will remain in the hospital under observation per standard hospital practice. Following hospital discharge, the subject will be contacted by phone one week after Visit 2 and will be seen at the study site at one month after Visit 2. After the one month visit following Visit 2, the subject will be scheduled for the second LVRC placement in the contralateral lung to take place approximately 2 months after Visit 2. Only a single lung will be treated during any bronchoscopy.

After the subject's second LVRC placement procedure (Visit 5), the subject will remain in the hospital under observation per standard hospital practice. Following hospital discharge, the subject will be contacted by phone one week after Visit 5 and will be seen for the tests, procedures and follow-up described in Table 6. Subjects will be followed up annually for 5 years. After the 5 year visit, the subject will exit the study.

Table 6. Visit Schedule

Procedure / Assessment	Visit 1 Pre-Treatment (Screening)	Visit 2 LVRC Placement #1	Visit 3 1 Week post Visit 2 ^a (Phone Call)	Visit 4 1 Month post Visit 2 ^b (Office Visit)	Visit 5 LVRC Placement#2 (2 Month post Visit 2)	Visit 6 1 Week post Visit 5 ^a (Phone Call)	Visit 7 1 Month post Visit 5 ^b (Office Visit)	Visit 8 6 Months post Visit 2 ^c (Office Visit)	Visit 9 9 Months post Visit 2 ^a (Phone Call)	Visit 10 12 Months post Visit 2 ^c (Office Visit)	Visit 11 24 Months post Visit 2 ^c (Office Visit)	Visit 12 36 Months post Visit 2 ^c (Office Visit)	Visit 13 48 Months post Visit 2 ^c (Office Visit)	Visit 14 60 Months post Visit 2 ^c (Office Visit)
Informed Consent	X													
Inclusion/ Exclusion	X													
Focused physical exam including vital Signs andSpO ₂	X	X		X	X		X	X		X	X	X	X	X
Record the following measures from the 12 Month RENEW Visit in the eCRF as baseline measurements: Spirometry, Lung Volumes and Diffusing Capacity, 6MWT, SGRQ, mMRC*		X												
Spirometry	X							X		X	X	X	X	X
Lung Volumes and Diffusing Capacity	X*							X		X	X	X	X	X
6MWT	X*			X			X	X		X	X	X	X	X
SGRQ	X*			X			X	X		X	X	X	X	X
mMRC	X*			X			X	X		X	X	X	X	X
Blood panel and ABG	X													
EKG	X													
Echocardiogram†	X													
Concomitant Medication / O ₂ Use	X	X	X	X	X	X	X	X	X	X	X	X	X	X
Pregnancy Testing	X	X			X				X					
CT Scan	X									X				
Chest X-Ray	X	X†			X†									
Bronchoscopy / Coil Placement		X			X									
Take subject status ^d			X	X	X	X	X	X	X	X	X	X	X	X
Exit Study														X

^a±3 days^b Minus 2 weeks to plus 4 weeks^c ±4 weeks

* If 12 Month RENEW Visit occurred within 6 weeks of Visit 1, use 12 Month RENEW values for lung volumes, diffusing capacity, SGRQ, 6MWT, and mMRC as baseline measurements. If 12 Month RENEW Visit occurred more than 6 weeks before Visit 1, perform these tests and record results as baseline measurements.

† Chest x-ray #1 is done immediately post-procedure and chest x-ray #2 is done prior to discharge.

^d includes a review of subject's medicines, O₂ use and AE assessment

‡ May use any echocardiogram taken within 6 months of Visit 1

5 Study Subject Recruitment

All study subjects will be patient volunteers who completed the Lung Volume Reduction Coil Treatment in Patients with Emphysema (RENEW) Study as Control Subjects and who meet the inclusion / exclusion criteria including a willingness to read, understand, and sign the Informed Consent.

5.1 Inclusion Criteria

Subjects must meet **all** of the following inclusion criteria to be entered into the study:

1. Subject was enrolled as a Control Subject in and completed all required study assessments through the 12 Month visit for the Lung Volume Reduction Coil Treatment in Patients with Emphysema (RENEW) Trial, CLN0009.
2. Subject has post-bronchodilator FEV₁ ≤45% predicted.
3. Subject has residual volume (RV) ≥175% predicted.
4. Subject has stopped smoking for at least 8 weeks prior to entering the study, as confirmed by a Cotinine test or other appropriate diagnostic test.
5. Subject read, understood and signed the Informed Consent form.
6. Subject has received Pneumococcal and Influenza vaccinations consistent with local recommendations and/or policy.

5.2 Exclusion Criteria

Subjects will be excluded from the study if any of the following conditions apply:

1. Subject has severe homogeneous emphysema as determined by the Core Radiology Lab
2. Subject has co-morbidities that may significantly reduce subject's ability to improve exercise capacity (e.g. severe arthritis, planned knee surgery) or baseline limitation on 6MWT is not due to dyspnea.
3. Subject has a change in FEV1 >20% (or, for subjects with pre-bronchodilator FEV1 below 1 L, a change of > 200 mL) post-bronchodilator, unless investigator can confirm by other means that subject does not have asthma.
4. Subject has DLCO <20% of predicted.
5. Subject has severe gas exchange abnormalities as defined by:
PaCO₂ >55 mm Hg
PaO₂ <45 mm Hg on room air (High altitude criterion: PaO₂ <30 mm Hg)
6. Subject has a history of recurrent clinically significant respiratory infections, defined as 3 hospitalizations for respiratory infection during the year prior to enrollment.
7. Subject has severe pulmonary hypertension. If pulmonary hypertension is present, "severe" is defined by right ventricular systolic pressure >50 mm Hg via right heart catheterization and/or echocardiogram.
8. Subject has an inability to walk >140 meters (150 yards) in 6 minutes.
9. Subject has evidence of other severe disease (such as, but not limited to, lung cancer or renal failure), which in the judgment of the investigator may

compromise survival of the subject for the duration of the study.

10. Subject is pregnant or lactating, or plans to become pregnant within the study timeframe.
11. Subject has an inability to tolerate bronchoscopy under moderate sedation or general anesthesia.
12. Subject has clinically significant bronchiectasis.
13. Subject has giant bullae >1/3 lung volume.
14. Subject has had previous LVR surgery, lung transplantation, lobectomy, LVR devices or other device to treat COPD in either lung.
15. Subject has been involved in pulmonary drug or device studies within 30 days prior to this study, with the exception of the RENEW Study.
16. Subject is taking >20 mg prednisone (or equivalent dose of a similar steroid) daily.
17. Subject requires high level chronic immunomodulatory therapy to treat a moderate to severe chronic inflammatory autoimmune disorder.
18. Subject is on an antiplatelet (such as Plavix) or anticoagulant therapy (such as heparin or Coumadin) which cannot be stopped for seven (7) days prior to procedure.
19. Subject has a sensitivity or allergy to nitinol (nickel-titanium) or its constituent metals.
20. Subject has a known sensitivity to drugs required to perform bronchoscopy.
21. Subject has been diagnosed with alpha-1 antitrypsin deficiency (AATD).
22. Subject has any other disease, condition(s) or habit(s) that would interfere with completion of study and follow up assessments, would increase risks of bronchoscopy or assessments, or in the judgment of the investigator would potentially interfere with compliance to this study or would adversely affect study outcomes.

6 Study Plan

6.1 Investigator Training

Investigators will have been trained in the proper use and operation of the Coil System and may have performed Coil procedures as part of the Lung Volume Reduction Coil Treatment in Patients with Emphysema (RENEW) Study before initiation of any treatment. If necessary, additional training will be provided.

PneumRx personnel will be available to provide any additional technical support during treatment sessions until the investigator and his/her team feel comfortable with the use of the device.

NOTE: All assessments by investigators or other healthcare professionals will be performed to the same standards (ATS Guidelines) as those in the pivotal protocol as detailed in the Study Operational Instructions.

6.1.1 Informed Consent

- Provide information to the potential subject and review Informed Consent Form details. Obtain Informed Consent in writing from the subject as part of Pre-treatment/Baseline Screening (Visit 1).

- Provide the subject with a copy of the signed Informed Consent Form for their records.

6.1.2 Study Identification Number

- Assign the subject a unique study identification number (Study ID number) after signing of Informed Consent.

6.1.3 Pre-treatment/Screening Evaluations

Perform the following evaluations during the Pre-treatment Screening (Visit 1):

- Detailed medical history, to include the number of years the subject has been diagnosed with emphysema, other significant illnesses, current smoking status and history, medications, O₂ use, etc.
- Vital signs and pulmonary assessment, including SpO₂ and breath sounds.
- Resting Electrocardiogram (EKG).
- Echocardiogram, or review echocardiogram taken within the past 6 months.
- Blood panel to assess inclusion exclusion criteria and ability to undergo anesthesia (to include Hemoglobin, Hematocrit, White Blood Cell (WBC), Platelet count, Prothrombin Time/International Normalized Ratio (PT/INR), Sodium, Potassium, Chloride, Glucose, Total Protein, Albumin, Blood Urea Nitrogen (BUN), and Creatinine.).
- Cotinine or other appropriate diagnostic test
- Pregnancy test for females of child-bearing potential prior to radiographic procedures.
- Room air Arterial Blood Gasses (ABG).
- Chest x-ray.
- CT Scan collected per guidelines provided by the Core (Radiology) Lab Protocol.
- Pre- and post-bronchodilator spirometry

If screening performed more than 6 weeks after subject's 12 Month Visit in the RENEW study, also perform the following:

- Pre- and post-bronchodilator spirometry
- Post-bronchodilator lung volume measurements by plethysmography
- Diffusing Capacity (DLCO)
- Modified Medical Research Council (mMRC) dyspnea scale
- 6 Minute Walk Test
- St. George's Respiratory Questionnaire (SGRQ)

6.2 Treatment

6.2.1 Visit 2 - LVRC Placement

- Perform pregnancy test for females of child bearing potential prior to radiographic procedures.
- Prepare subject for bronchoscopy per standard hospital practice.

- Unless contraindicated, prescribe a prophylactic regimen of antibiotics to be taken for at least seven (7) days after the procedure and steroids to be taken two (2) days before and at least seven (7) days after the procedure.
- Administer general anesthesia or sedation to perform Coil placement. All local institutional policies relevant to general anesthesia and/or sedation should be observed.
- Insert the bronchoscope per the manufacturer's instructions.
- If not already documented, perform bronchoalveolar lavage and send sample for culture and Gram stain to document any host pathogens.
- Navigate the bronchoscope and identify the airways in one of the lobes identified by the CT Core Lab as a lobe to be treated.
- Deliver the Coils in accordance with RePneu Coil System Instructions for Use.
- Only place the devices unilaterally. DO NOT place the devices in both the right and left lungs during one bronchoscopy session.
- Allow the Subject to recover from anesthesia and monitor as per standard hospital practice.

6.2.2 Visit 2, cont: Post Bronchoscopy Monitoring and Evaluations

- Complete a chest x-ray post-procedure.
- Record AEs (See Section 7).
- Maintain subject in hospital for observation per standard hospital practice.
- Complete a second chest x-ray prior to discharge
- Discuss maintenance rehabilitation activity plan with subject.
- Provide detailed instructions to Subject on expected effects of Coil procedure and instruct the Subject to contact the Site and Principal Investigator immediately should any of the effects be experienced.

6.2.3 Visit 3 - 1 Week Post Visit 2 Follow Up Phone Call

- Contact Subject via telephone 1 week after Visit 2 to assess status.
- Review medications and O₂ use.
- Record AEs (See Section 7).
- Discuss maintenance rehabilitation activity plan.

6.2.4 Visit 4 - 1 Month Post Visit 2 Follow Up

- Perform focused pulmonary assessment including Vital Signs (heart rate, blood pressure, temperature, respiratory rate, SpO₂) and breath sounds.
- Perform 6MWT
- Administer SGRQ
- Administer mMRC
- Review medications and O₂ use.

- Record AEs since last follow-up (See Section 7).
- Discuss maintenance rehabilitation activity plan.

6.2.5 Visit 5 - 2 Months Post-Visit 2 LVRC Placement #2

- During Coil placement procedure #2, the investigator will treat the contra-lateral lung.
- Perform pregnancy test for females of child-bearing potential prior to radiographic procedures.
- Unless contraindicated, prescribe a prophylactic regimen of antibiotics to be taken for at least seven (7) days post-procedure and steroids to be taken two (2) days before and at least seven (7) days after treatment.
- Prepare subject for bronchoscopy per standard hospital practice.
- Administer general anesthesia or sedation to perform Coil placement. All local institutional policies relevant to general anesthesia and/or sedation should be observed.
- Insert the bronchoscope per manufacturer's instructions.
- Navigate the bronchoscope and identify the airways in one of the lobes identified by the CT Core Lab as a lobe to be treated
- Deliver the Coils in accordance with the RePneu Coil System Instructions for Use.
- Only place the Coils unilaterally. DO NOT place the devices in both the right and left lungs during one bronchoscopy session.
- Allow the Subject to recover from anesthesia and monitor as per standard hospital practice.

6.2.6 Visit 5, cont: Post Bronchoscopy Monitoring and Evaluations

- Conduct chest x-ray.
- Record AEs (See Section 7).
- Maintain Subject at the hospital for observation per standard hospital practice.
- Conduct another chest x-ray prior to discharge.
- Discuss maintenance rehabilitation activity plan with Subject.
- Provide detailed instructions to Subject on expected effects of Coil procedure and instruct the Subject to contact the Site and Principal Investigator immediately should any of the effects be experienced.

6.2.7 Visit 6 - 1 Week Post Visit 5 Phone Call

- Contact Subject via telephone 1 week after Visit 5 to assess status.
- Review medications and O₂ use.
- Record AEs (See Section 7).
- Discuss maintenance rehabilitation activity plan with Subject.

6.2.8 Visit 7 - 1 Month Post Visit 5 Follow Up

- Perform focused pulmonary assessment including Vital Signs (heart rate, blood pressure, temperature, respiratory rate, SpO₂) and breath sounds.
- Perform 6MWT
- Administer SGRQ
- Administer mMRC
- Review medications and O₂ use.
- Record AEs since last follow-up (See Section 7).
- Discuss maintenance rehabilitation activity plan with Subject.

6.2.9 Visit 8 - 6 Months Post Visit 2 Follow Up

- Perform focused pulmonary assessment including Vital Signs (heart rate, blood pressure, temperature, respiratory rate, SpO₂) and breath sounds.
- Perform post-bronchodilator spirometry.
- Perform Lung Volumes and DLCO
- Perform 6MWT
- Administer SGRQ
- Administer mMRC
- Review medications and O₂ use.
- Record AEs since last follow-up (See Section 7).
- Discuss maintenance rehabilitation activity plan with Subject.

6.2.10 Visit 9 - 9 Months Post Visit 2 Phone Call

- Contact Subject via telephone 1 week after bronchoscopy session / LVRC procedure to assess status.
- Review medications and O₂ use.
- Record AEs (See Section 7).
- Discuss maintenance rehabilitation activity plan with Subject.

6.2.11 Visit 10 - 12 Months Post Visit 2 Follow Up

- Perform focused pulmonary assessment including Vital Signs (heart rate, blood pressure, temperature, respiratory rate, SpO₂) and breath sounds.
- Perform pregnancy test for females of child-bearing potential prior to radiographic procedures.
- Perform post-bronchodilator spirometry.
- Perform Lung Volumes and DLCO
- Perform 6MWT
- Administer SGRQ
- Administer mMRC

- Review medications and O₂ use.
- Record AEs since last follow-up (See Section 7).
- Discuss maintenance rehabilitation activity plan with Subject.
- Take Chest CT

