	
use and record AEs.
 
Visit 7: 1 Month post Visit 5Perform focused physical exam including Vital Signs (heart rate, blood pressure, temperature, respiratory rate, SpO₂) and breath sounds and 6MWT, administer SGRQ and mMRC. Review medications and O₂ use, Record AEs since last follow-up.
 
Visit 8: 6 Months post Visit 2 Perform focused physical exam including Vital Signs (heart rate, blood pressure, temperature, respiratory rate, SpO₂) and breath sounds, post-bronchodilator spirometry, lung volumes, DLCO and 6MWT; administer SGRQ and mMRC. Review medications and O₂ use, Record AEs since last follow-up.
 
Visit 9: 9 Months post Visit 2 Follow Up Phone Call/interview to assess subject overall status. Review medications and O₂ use and record AEs.
 
Visit 10: 12 Months post Visit 2 Perform focused physical exam including Vital Signs (heart rate, blood pressure, temperature, respiratory rate, SpO₂) and breath sounds, post-bronchodilator spirometry, lung volumes, DLCO and 6MWT; administer SGRQ and mMRC. Review medications and O₂ use, Record AEs since last follow-up. CT scan.
 
Visit 11: 24 Months post Visit 2, Visit 12: 36 Months post Visit 2, and Visit 13: 48 Months post Visit 2 Perform focused physical exam including Vital Signs (heart rate, blood pressure, temperature, respiratory rate, SpO₂) and breath sounds, post-bronchodilator spirometry, lung volumes, DLCO and 6MWT, administer SGRQ and mMRC. Review medications and O₂ use, Record AEs since last follow-up.
 
Visit 14: 60 Months post Visit 2 Perform focused physical exam including Vital Signs (heart rate, blood pressure, temperature, respiratory rate, SpO₂) and breath sounds, post-bronchodilator spirometry, lung volumes, DLCO and 6MWT; administer SGRQ and mMRC. Review medications and O₂ use, Record AEs since last follow-up. Exit study.

--	---

Management of Adverse Events	AE information will be collected throughout the study. Adverse events will be recorded on the AE eCRF by the investigator or authorized designee. Event, date of onset, severity, duration, and relationship to the procedure/device will be recorded. All adverse events will be followed until they are adequately resolved or stabilized or for 1 month following study completion or termination, whichever comes first.
Statistical Analyses	Descriptive statistics will be used to evaluate the data, including differences from Baseline to 12 months in 6MWT and SGRQ, and safety.

2 Introduction

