1.4 Sample Size and Power Calculation

The CROSSOVER Study was designed to provide an opportunity for qualifying Control subjects from the RENEW study to receive the LVRC treatment once their participation in the randomized phase of the RENEW study was complete; all qualifying subjects who wished to participate and met the enrollment criteria were enrolled. Thus, the study sample size was not based on a primary and null hypothesis, or power calculation and results will only be presented descriptively.

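### Table 6 shows no pregnancy test at the Visit 10 CT and marks one at the Visit 9 phone call, at odds with Protocol 6.2.10 and 6.2.11

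*Protocol*

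**What the plan says.** The protocol describes Visits 9 and 10 in three places.

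- **Visit text.** Section 6.2.11 (Visit 10) lists a chest CT and instructs: "Perform pregnancy test for females of child-bearing potential prior to radiographic procedures". The section headed "6.2.10 Visit 9 - 9 Months Post Visit 2 Phone Call" has four bullets, none of them a pregnancy test or imaging.
- **Table 6 (in 4.6.1).** The row labelled "Pregnancy Testing" is marked at Visits 1, 2, 5 and 9. The CT row is marked at Visits 1 and 10. The column headers make Visit 9 a phone call and Visit 10 an office visit.
- **Synopsis.** It gives "Visit 9: 9 Months post Visit 2 Follow Up Phone Call/interview to assess subject overall status", followed by medication, oxygen and adverse-event review. Its Visit 10 entry includes the CT scan and no pregnancy test.

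Section 4.6.1 points sites to Table 6 for what is done after the second coil placement. Section 6.2.15 (Visit 14) also carries a bullet for a pregnancy test before radiographic procedures.

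**The concern.** In Table 6 a test is marked at a contact made by telephone, where no imaging is planned, and none is marked at the office visit where a CT is planned. The visit text has the reverse. Elsewhere in section 6 the protocol ties the test to imaging, and section 9.1 lists radiation exposure among the risks, so the mismatch touches a safety precaution.

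The table matters because it is operative text: 4.6.1 refers sites to it. Schedules and case report forms are often built from such a table. At stake is whether a woman of child-bearing potential might have the 12-month CT without the test that 6.2.11 calls for.

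**Working it through.** No sample-size or error-rate calculation applies. The check is a column count and a comparison of texts.

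**1. Column count.** Table 6 has 14 visit columns. Thirteen of its rows were counted and each has 14 cells. The relevant marks are:

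- pregnancy testing: Visits 1, 2, 5, 9
- CT scan: Visits 1, 10
- chest x-ray: Visits 1, 2, 5
- bronchoscopy: Visits 2, 5

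**2. Table against visit text.**

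| Visit | Table 6: test | Table 6: imaging | Section 6: test | Section 6: imaging |
|---|---|---|---|---|
| 1 | yes | CT, x-ray | yes (6.1.3) | CT, x-ray |
| 2 | yes | x-ray | yes (6.2.1) | x-ray |
| 5 | yes | x-ray | yes (6.2.5) | x-ray |
| 9 | **yes** | none | **no** (6.2.10) | none |
| 10 | **no** | CT | **yes** (6.2.11) | CT |
| 14 | **no** | none | **yes** (6.2.15) | none |

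Table and text agree at Visits 1, 2 and 5 and disagree at Visits 9, 10 and 14. Within the table, Visit 10 is the only imaging visit without a test, and Visit 9 is the only test visit without imaging or attendance.

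**3. Could the mark have moved in reading the PDF?** The first three pregnancy marks match the text, so the row as a whole has not shifted. The CT, spirometry, 6MWT, bronchoscopy and exit rows also fall on the visits that the text gives. An artefact would have to move one mark by one cell and still leave 14 cells. That is unlikely but not excluded.

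**4. What does not depend on column position.** The table row has 4 marks. The visit text calls for 5 tests (Visits 1, 2, 5, 10, 14). If the fourth mark really sits at Visit 10, the conflict at Visits 9 and 10 disappears and only Visit 14 is left unmatched.

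**5. Size of the gap.** Visit 5 is planned about 2 months after Visit 2, and Visit 10 is 12 months after Visit 2 with a window of ±4 weeks. The interval is 12 − 2 = 10 months, or roughly 9 to 11 months across the Visit 10 window if Visit 5 falls at month 2.

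**The case against.** **Section 6.2.11 is plain.** It puts the test and the CT in the same visit list, and the link between test and imaging is also stated for Visits 1, 2 and 5. A reader might infer from the table that sites would scan without testing. The documents do not support that: a site that reads 6.2.11 sees the test. The risk is confined to a site relying on the table or synopsis alone, so the word is could.

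**The table is not tidy elsewhere.** The row for recording the RENEW values is marked at Visit 2, whereas the synopsis and the table's own asterisk note tie those values to Visit 1. The echocardiogram row carries the chest x-ray footnote symbol. This gives some reason to doubt the position of a single mark, and it stands as a reason to check the typeset page first.

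**The synopsis is abbreviated.** It mentions pregnancy testing at no visit, so its silence at Visit 10 is an omission and not a competing instruction. That is fair. It still means the synopsis does not correct the table.

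**Other inferences go too far.**

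- Exclusion 10 (pregnancy) governs entry. The Visit 10 test is a precaution during follow-up, so the exclusion adds no weight.
- A reader might expect sites following either source to be recorded as deviating from the other. SAP 2.6 tabulates deviations, but by a deviation plan that is not part of these documents, and nothing says that following explicit visit text is a deviation.
- Visit 14 might be read as a second safety gap. No imaging is scheduled there, so the bullet is at most conditional, redundant or left over.

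**Conclusion.** The point holds as a minor internal inconsistency. As supplied, Table 6 conflicts with 6.2.10 and 6.2.11 at Visits 9 and 10. A site using the table or synopsis alone could take the 12-month CT about 10 months after the last test scheduled at an attended visit.

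The conclusion rests on two assumptions. The first is that the fourth mark is at Visit 9 on the typeset page; if it is at Visit 10, only the synopsis omission and the Visit 14 mismatch remain. The second concerns how many subjects are affected. The documents give no count of women of child-bearing potential, and the number could be zero. Section 2.2 notes that most emphysema patients are of advanced age, so it is probably small.

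No endpoint, analysis or estimate changes. SAP 1.4 states: "Thus, the study sample size was not based on a primary and null hypothesis, or power calculation and results will only be presented descriptively".

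The Visit 14 mismatch is a separate editorial point without a safety consequence on the planned schedule.

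**What to change.** 1. Confirm the position of the fourth pregnancy-testing mark on the typeset page of Table 6.
2. If it is at Visit 9, reconcile the Table 6 row and the synopsis with 6.2.10 and 6.2.11, so that all of them agree on whether and when a test is done at Visits 9 and 10 relative to the CT. The choice of rule is a clinical one for the sponsor and is not proposed here.
3. Align the eCRF visit forms with the agreed schedule and send sites the corrected table.
4. Separately, reconcile the pregnancy-test bullet in 6.2.15 with Table 6 at Visit 14.

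The cost is one table row, a line in the synopsis, possibly one bullet in the visit text, and a check of the forms. No new type of procedure is needed, and the SAP does not change.
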